12.6 Analysis of exploratory endpoints

12.6.1 PFS2

PFS2 is defined as time from date of randomization to the first documented local progression on next-line therapy or death from any cause, whichever occurs first. The first documented progression on next-line treatment is based on investigator assessment of PD (i.e. as captured on the anti-neoplastic therapy after treatment discontinuation eCRF page); it is not necessary to continue to collect tumor assessments data for subsequent anti-neoplastic therapies for the purpose of PFS2.

- Next-line therapy is defined as the first new (systemic) anti-neoplastic therapy initiated after discontinuation of study treatment regardless of EoT reason. Drugs given as part of the same regimen should be considered as first line (i.e. part of the next-line therapy).
- New anti-neoplastic therapies after EoT will be collected in the anti-neoplastic therapy after treatment discontinuation eCRF page including start/end date, reason for discontinuation, date and type of progression («clinical» vs «radiologic»).
- PFS2 will be censored if no PFS2 event (progression or death) is observed during next-line therapy before the analysis cut-off date; the censoring date will be the last contact date.
- However, in case a second new anti-neoplastic therapy is introduced without prior PFS2 event, then PFS2 will be censored at the end date of the first new anti-neoplastic therapy (i.e. next line therapy).
- Any death prior to initiation of next-line therapy will be considered as an event for PFS2. Any death occurring following end of next line therapy will be considered as an event if no second new anti-neoplastic therapy has been introduced.

• PFS and PFS2 may be identical if a subject did not experience an event (i.e. progression) prior to initiation of next-line therapy, and adequate tumor assessments continue until RECIST 1.1-documented disease progression after initiation of next-line therapy.

PFS2 will be analyzed in the FAS population according to the randomized treatment group and strata assigned at randomization. The PFS2 distribution will be estimated using the Kaplan-Meier method, and the Kaplan-Meier curves, medians and 95% confidence intervals of the medians will be presented for each treatment group. The hazard ratio for PFS2 will be calculated, along with its 95% confidence interval, using a stratified Cox model.

Time to Second Progression (PFS2) in the two treatment arms will be evaluated as a secondary endpoint. This endpoint is defined as the time in months from the first progression to the second progression or death. The date of both the first and second progression will be derived programmatically through the RECIST criteria.

It is recognized that due to cross-over, the lower scan frequency (every six months) after PEP, and, the relatively short follow-up, the possibility to draw firm conclusions is limited.

12.6.2 Patient reported outcomes not associated with key secondary endpoint

TTD for items/scales derived from EORTC QLQ-G.I.NET21 and EORTC QLQ-30 not included among the key secondary endpoints will be analyzed as exploratory endpoints. The TTD distribution will be estimated using the Kaplan-Meier method, and the Kaplan-Meier curves, medians and 95% confidence intervals of the medians will be presented for each treatment group. The hazard ratio for TTD will be calculated, along with its 95% confidence interval, using a stratified Cox model.

Quality of Life will also be assessed in terms of change from baseline in EORTC QLQ-G.I.NET21, EORTC QLQ-C30 and EQ-5D-5L through Mixed Model Repeated Measures (MMRM), which deals with missing values in a model based way, and implicitly imputes missing data under a missing at random assumption. The model will include the explanatory variables Treatment, Baseline, Week, and, the interaction between Treatment and Week. A test of treatment effect is performed at each week, and, overall.

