In accordance with the recently finalized guidance for industry on considerations for the inclusion of adolescent patients in adult oncology clinical trials and the consensus expert opinion presented by the European multi-stakeholder platform ACCELERATE to include adolescents in adult oncology clinical trials when the histology and biologic behavior of the cancer under investigation is the same in, or the molecular target of the drug is relevant to, cancers in both adult and adolescent patients (FDA guidance), this study will include adolescents ≥ 15 years and >40 kg BW. Even though the number of adolescents ≥ 15 years fulfilling the inclusion criteria for this study is very small, the high unmet medical need in this population is justifying their enrollment. It is not

expected that adolescents below the age of 15 years will present with the disease meeting the inclusion criteria for this study.

Due to the radioactive nature of Lutathera and its method of infusion, and similarly to the NETTER-1 trial design, it is not possible to implement a fully double-blinded design for this study, however a central, blinded, real-time IRC (Independent Review Committee) assessment is implemented to ensure an independent evaluation of the tumor response according to RECIST 1.1 criteria.

Randomization will be stratified by Grade (G2 vs G3) and tumor origin (pNET vs other origin), preventing imbalance between treatment groups for known factors that influence prognosis.

For this trial a 2:1 randomization design is chosen to allow patients to have a higher chance of getting the treatment which is anticipated to be more effective. For the same reason and to minimize the possible higher drop-out rate in the control arm, patients will be offered to cross-over to Lutathera after centrally confirmed RECIST progression (or locally confirmed if it occurs after Week 72 post the primary end point analysis).

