- Using the primary analysis source on the FAS and including TTD events whenever they occur, even after two or missing QoL assessments. In the summary tables, this approach is referred to as ‘actual event TTD supplementary analyses’.

For this supplementary analyses, all analyses will be conducted using stratified Cox proportional hazards model. If there are not enough events in all strata, the analysis will be conducted using an unstratified Cox proportional hazards model.

Quality of life will also be assessed in terms of change from baseline through Mixed Model Repeated Measures (MMRM), which are outside the scope of the primary analysis, and will be conducted in the final analysis.

Subgroup analyses for TTD

If the primary analysis is statistically significant, as well as the key secondary ORR analysis and the TTD QoL analyses are statistically significant, to assess the homogeneity of the treatment effect across demographic and baseline disease characteristics, subgroup analysis for TTD will be performed. Please refer to [Section 2.2.3](#) for detailed subgroup definitions.

For each of the subgroups, the following analyses will be performed:

- Median Kaplan-Meier estimates of the survival distribution of TTD
- Hazard ratio with 95% CI using unstratified Cox proportional hazards model.

Efficacy analyses in subgroups are intended to explore the consistency (homogeneity) of treatment effect. Forest plot (including sample size/number of TTD events and HR with 95% CI) will be produced to graphically depict the treatment effect estimates in different subgroups. No inferential statistics (p-values) will be produced for the subgroups.

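### The exploratory quality-of-life MMRM omits the randomization factors, so its reported standard errors are likely to be somewhat too large

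*Protocol*

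**What the plan says.** Protocol 12.6.2 is the only place where the terms of the MMRM are given: "The model will include the explanatory variables Treatment, Baseline, Week, and, the interaction between Treatment and Week". It adds that "A test of treatment effect is performed at each week, and, overall". The same section states that the model handles missing values under a missing-at-random assumption. Its preceding paragraph, on time to deterioration (TTD), uses the strata: "The hazard ratio for TTD will be calculated, along with its 95% confidence interval, using a stratified Cox model".

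The SAP adds no terms. Section 2.6.6 says "Quality of life will also be assessed in terms of change from baseline through Mixed Model Repeated Measures (MMRM"), and that these analyses are ones "which are outside the scope of the primary analysis, and will be conducted in the final analysis". Section 2.7.1 says only that change from baseline in the other questionnaires will be explored. Section 5.4 (statistical models) contains no MMRM, and section 4 declares no change to the protocol's analyses.

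On the design, Protocol 4.1 says "Randomization will be stratified by Grade (G2 vs G3) and tumor origin (pNET vs other origin"), with the aim of "preventing imbalance between treatment groups for known factors that influence prognosis".

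**The concern.** When allocation is stratified on factors related to the outcome, the treatment estimate varies less from trial to trial than a model without those factors believes. The omitted factors stay in the residual variance, so the model reports a standard error that is too large. The rest of the plan avoids this: PFS, ORR, and key secondary and exploratory TTD are all analysed with stratification. No reason is given for treating the MMRM differently.

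Missing data are the second issue. Routine 12-weekly QoL collection runs to the end of treatment (Protocol 8.4), and treatment ends at centrally assessed progression (Protocol 3.2). The protocol regards grade as prognostic. A fully observed baseline factor that plausibly predicts who stops contributing QoL data is therefore outside the model.

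At stake are the width of intervals and the behaviour of week-by-week tests in an exploratory analysis.

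**Working it through.** **The plan's own figure.** The only sizing figure is 99 PFS events (Protocol 12.8.1). With HR 0.50, one-sided 2.5%, 90% power and 2:1 allocation: (1.960 + 1.282)² / [(2/9) × (ln 0.5)²] = 98.4, rounded up to 99. The critical hazard ratio is exp(−1.960/√(99 × 2/9)) = 0.658, as stated. Neither depends on the MMRM. No SD, correlation, power or precision figure is given for QoL, so everything below is a range under assumptions.

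**Effect of the strata on the reported standard error.** Let R² be the share of residual variance at one visit explained by the four grade-by-origin cells, after baseline QoL. The reported SE is multiplied by √(1 − R²). Reading R² as an in-sample share, three extra degrees of freedom change the residual degrees of freedom from 222 − 3 = 219 to 216. This multiplies the SE by √(219/216) = 1.007, the cost of about 0.7%.

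| Assumed R² | √(1 − R²) | Fall in reported SE | After the 0.7% cost | Net change |
|---|---|---|---|---|
| 1% | 0.995 | 0.5% | 1.002 | +0.2% |
| 5% | 0.975 | 2.5% | 0.981 | −1.9% |
| 10% | 0.949 | 5.1% | 0.955 | −4.5% |
| 15% | 0.922 | 7.8% | 0.928 | −7.2% |

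**Reported versus true precision.** Simulated MMRMs used 148/74 patients, stratified 2:1 allocation, six visits 12 weeks apart, SD 20, visit-to-visit correlations of 0.45 to 0.69, strata shares of 35/30/20/15%, R² = 5%, 3% loss per visit and 700 runs for each of two baseline-correlation patterns. Adding the strata changed:
- the model-reported SE by −2.3% to −3.2% at single weeks and −4.6% to −5.3% for the overall effect;
- the empirical SE of the estimate by 0.5% or less.

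Without strata, the reported SE exceeded the empirical SE in all six comparisons (ratios 1.01 to 1.09). With strata the ratios ran from 0.96 to 1.06. The empirical SEs carry Monte Carlo error of about 1/√(2 × 700) = 2.7%, so the paired changes are firmer evidence than any single ratio. The fits used maximum likelihood, which does not charge for the extra terms: in a smaller set (60 runs per scenario, 15% loss per visit) with R² = 0, the reported SE still fell by 0.3% to 0.7%. Part of the simulated fall is therefore not real gain.

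**Missing data.** As an illustration, take the design medians of 15 and 30 months, exponential progression times, QoL ending at progression and 35% G3 at entry (assumed). The G3 share among patients still observed at week 72 would be:
- G3:G2 progression hazard ratio 1.5: 28% control, 31% Lutathera;
- hazard ratio 2: 23% and 29%;
- hazard ratio 3: 16% and 25%.

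Balance at entry can therefore drift apart at late visits. Baseline and earlier QoL scores, already in the model, recover part of this.

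**Baseline-by-week.** In the same 700-run simulations, adding this term changed the reported SE by 0 to 0.3% when the correlation with baseline fell from 0.6 to 0.5. When it fell from 0.6 to 0.3, the reductions were 2.2% at the last visit, 0.4% overall and 0.1% at week 24.

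**The case against.** The strongest reply is that nothing rests on this model. The protocol lists it under "12.6 Analysis of exploratory endpoints"; the SAP makes it supplementary and defers it. It is outside the hierarchy of PFS, ORR and four TTD scales, has no alpha or power target, and the confirmatory QoL comparisons already use the strata. The error is also in the safe direction. All of this stands, and it limits the point to a minor one.

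Nor do the documents show that grade and origin predict QoL once baseline QoL is in the model; they call them prognostic, which is a different claim. This stands too, and is why the range must reach down to no gain.

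Three stronger readings are tempting and should be resisted:
- A reader might infer that the trial throws away substantial precision. Stratified allocation has already secured the balance; what is lost is mainly the credit for it in the reported SE.
- A reader might infer that adding grade makes dropout ignorable. Progression is a post-baseline event, and baseline grade does not put it in the model. Grade helps only so far as it predicts unobserved QoL beyond the observed scores, which the documents do not establish.
- A reader might treat the missing baseline-by-week term as a defect. Nothing in the documents shows that the baseline slope drifts. The term adds a parameter per visit, while SAP Table 2.1-1 lets visits continue every 12 weeks with no fixed end and the control arm has 74 patients, so late visits may be too sparse to support it.

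**Conclusion.** The omission is real, the SAP does not repair it, and it is inconsistent with the stratified analyses around it. Its likely effect is a modestly overstated standard error. Adding the strata would lower the reported SE by about 0.5% to 8% for an assumed R² of 1% to 15%, before the degrees-of-freedom cost, with no net gain at 1%. At an assumed R² of 5%, true sampling precision changes by 0.5% or less. Missing-at-random becomes somewhat more plausible with grade in the model, to an extent that cannot be quantified from the documents. This is a refinement to an exploratory analysis; the 99 events, the 222 patients and every primary and key secondary conclusion are unaffected.

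**What to change.** Before the final analysis, give the MMRM a full specification in the SAP: the protocol's terms plus grade (G2/G3) and tumor origin (pNET/other), as assigned at randomization, as fixed effects. The same paragraph should state the covariance structure and degrees-of-freedom method, which the SAP also leaves open. Main effects alone cost two degrees of freedom; using all four cells costs three. Baseline-by-week can be left optional; if it is used, say how sparse late visits will be handled.

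The cost is a short SAP amendment and a small change to the model code for each scale. No new data, patients or procedures are needed, and because the MMRM is deferred to the final analysis, the change can be made before it is run.

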12.6.3 Pharmacokinetics

Patients in the control arm (all countries except for China) will yield PK data from blood sampling performed at pre-dose with respect to the octreotide long-acting i.m. injection for the 2nd, 4th, 5th and 7th treatment cycle (that is respectively at week 4, 12, 16 and 24) for the determination of plasma trough levels. Data will be processed using a population based model, for exploratory purposes. More details on the presentation of results will be given in the SAP.

Additionally, descriptive statistics and graphical display of octreotide plasma concentrations during the course of treatment will presented by dose group. Exploratory analysis will be performed to assess the dose-exposure relationship. More details on the presentation of results will be given in the SAP.

12.6.4 Re-treatment with Lutathera

Safety will be presented in a similar manner to that in Section 12.5.3 for those participants who receive re-treatment with Lutathera during the re-treatment period. The re-treatment period lasts from the date of first administration of re-treatment with Lutathera to progression or death during the re-treatment period.

All information obtained on adverse events will be displayed by subject.

All vital signs data will be listed subject, and visit/time and if ranges are available, abnormalities (and relevant orthostatic changes) will be flagged. Summary statistics will be provided by visit/time.

All ECG data (as per local assessment) will be listed by subject and visit/time, abnormalities will be flagged. Summary statistics will be provided by visit/time.

All laboratory data will be listed by subject, and visit/time and if normal ranges are available abnormalities will be flagged. Summary statistics will be provided by visit/time. Shift tables using the low/normal/high/ (low and high) classification will be used to compare the latest assessment before re-treatment to the worst re-treatment value.

All efficacy analyses for ORR, DoR, PFS, PFS2, and OS will be descriptive. Definitions for ORR, DoR, and PFS (as per local assessment) are the same definitions in Section 12.5.2 except that the baseline will be based on the tumor assessment which demonstrated progression thus allowing re-treatment with Lutathera. Definitions for OS and PFS2 are the same to that in Section 12.5.2 and Section 12.6.1, respectively.

12.7 Interim analyses

An interim analysis with respect to OS will be performed at the time of the PFS final analysis. At this time point, only estimation of treatment effect will be performed (hazard ratio and its 95% confidence interval).

12.8 Sample size calculation

12.8.1 Primary endpoint(s)

The sample size calculation is based on the primary variable PFS. Assuming a median PFS in the control arm (High Dose octreotide long-acting (60 mg)) of approximately 15 months, it is hypothesized that treatment with Lutathera added to standard dose octreotide long-acting will result in a 50% reduction in the hazard rate (corresponding to an increase in median PFS from 15 months to 30 months).

To ensure 90% power to test the null hypothesis: PFS hazard ratio = 1, versus the specific alternative hypothesis: PFS hazard ratio = 0.50, it is calculated that a total of 99 PFS events need to be observed. This calculation assumes analysis by a one-sided log-rank test at the overall 2.5% level of significance, patients randomized to the two treatment groups in a 2:1 ratio. Assuming that enrolment will continue for approximately 22.2 months at a rate of 10 patients per month and a 15% dropout rate by the time of the final PFS analysis, a total of 222 patients (148 for Lutathera arm and 74 for the control arm) will need to be randomized to observe the targeted 99

PFS events at about 12.8 months after the randomization date of the last patient, i.e., 35 months after the randomization date of the first patient. If the final analysis is performed when the targeted 99 PFS events are observed, the observed hazard ratio will have to be < 0.658 which corresponds to a difference in median PFS of 7.8 months to declare statistical significance.

These calculations were made using the software package East 6.4.

Randomization will be stratified by Grade (G2 vs G3) and tumor origin (pNET vs other origin).

13 Ethical considerations and administrative procedures

13.1 Regulatory and ethical compliance

This clinical study was designed and shall be implemented, executed and reported in accordance with the ICH Harmonized Tripartite Guidelines for Good Clinical Practice, with applicable local regulations (including European Directive 2001/20/EC, US CFR 21), and with the ethical principles laid down in the Declaration of Helsinki.

13.2 Responsibilities of the investigator and IRB/IEC

Before initiating a trial, the investigator/institution must obtain approval/favorable opinion from the Institutional Review Board/Independent Ethics Committee (IRB/IEC) for the trial protocol, written informed consent form, consent form updates, subject recruitment procedures (e.g., advertisements) and any other written information to be provided to subjects. Prior to study start, the investigator is required to sign a protocol signature page confirming his/her agreement to conduct the study in accordance with these documents and all of the instructions and procedures found in this protocol and to give access to all relevant data and records to Advanced Accelerator Applications monitors, auditors, Advanced Accelerator Applications, IRBs/IECs, and regulatory authorities as required. If an inspection of the clinical site is requested by a regulatory authority, the investigator must inform Advanced Accelerator Applications immediately that this request has been made.

13.3 Publication of study protocol and results

The protocol will be registered in a publicly accessible database such as clinicaltrials.gov and as required in EudraCT. In addition, after study completion (defined as last patient last visit) and finalization of the study report the results of this trial will be submitted for publication and posted in a publicly accessible database of clinical trial results, such as the Advanced Accelerator Applications clinical trial results website and all required Health Authority websites (e.g. Clinicaltrials.gov, EudraCT etc.).

Advanced Accelerator Applications (AAA) follows the ICMJE authorship guidelines (www.icmje.org). Authors (including Sponsor associates who may qualify for authorship), must therefore satisfy all of the following ICMJE authorship criteria:

- 1. Substantial contributions to conception or design of the work; or the acquisition, analysis, or interpretation of data for the work; AND
- 2. Drafting the work or revising it critically for important intellectual content; AND
- 3. Final approval of the version to be published; AND
- 4. Agreement to be accountable for all aspects of the work in ensuring that questions related to the accuracy or integrity of any part of the work are appropriately investigated and resolved.

The key principles that will be followed for AAA-sponsored, research-related publications are:

- AAA supports the publication of study results for its innovative medicines in a timely manner, whatever their outcome. AAA policy is not to withhold, veto or suppress data. However, due consideration must be given to the rights of AAA to protect confidential and/or patentable information, and to the protection of personal information, in particular patient privacy.
- Review by AAA of draft publications by clinical investigators in advance of submission/presentation of publication is designed to:
 - Confirm the accuracy of the data
 - Verify that proprietary information is not being inadvertently disclosed
 - Secure intellectual property rights, as needed
 - Provide any relevant supplementary information
- Publication of partial data (unless planned in the protocol) is discouraged. As a matter of scientific rigor and fairness to all investigators involved in a clinical study, and in accordance with the Joint Position on the Publication of Clinical Trial Results in the Scientific Literature, issued by the International Federation of Pharmaceutical Manufacturers and Associations (IFPMA), European Federation of Pharmaceutical Industries and Associations (EFPIA), Japan Pharmaceutical Manufacturers Association (JPMA), and Pharmaceutical Research and Manufacturers of America (PhRMA), it is AAA policy for multicenter clinical studies that:
- The first publication in a journal, or a presentation at a congress, be based on consolidated data from all centers, analyzed as stipulated by the protocol and agreed upon by investigators before trial initiation.
- Multicenter trials are designed to take full account of data accumulated from all centers (sample sized, powered with appropriate error rates), and AAA discourages presenting or publishing data gathered from a single, or small group of centers, unless agreed to by study investigators (e.g., Study Steering Committee) and AAA. Center specific analyses have greater variability and lead to exaggerated observed-treatment effects that are inherently less reliable. Valid conclusions regarding the primary endpoint of a clinical trial can only be based on the analyses predefined by the protocol.
- Study results should be published according to the contracted protocol agreements.

